13.3.2. Final Analysis

13.3.2.1. Primary Analysis

The primary comparison of interest (and primary endpoint) is to determine whether the objective response rate to trametinib in cohort A (“high affinity” group) is less than or equal to a null hypothesized response rate of 5% versus an alternative response rate of 25%. No comparisons between treatments will be performed as there is a single arm in each cohort. The primary analysis of ORR will be performed following treatment of all patients for at least 8 weeks or have discontinued therapy.

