6.4. Study Completion

Study will be completed having met the study objectives, approximately 24 months after last subject first visit, or when all subjects have withdrawn from the study, whichever occurs first.

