7.1. Time and Events Table

This section consists of the Time and Events Table (Table 14) and supplemental footnotes to describe assessment windows and sequencing of study-specific assessments and procedures.

Table 14 Time and Events

STUDY PHASES ¹	SCR ²	TREATMENT-One Cycle=28 days			Follow up ³	
		D1	D15 ²¹	Continuation	EOT	Post EOT FU
Visit Window (Days)	-28	N/A	±3	±3	± 3	±7
CLINICAL ASSESSMENTS						
Informed Consent ⁴	X					
Baseline demographics	X					
Medical History	X					
Interim Medical History				Day 1 of each cycle		
Disease Characteristics	X					
Prior Anti-Cancer Therapy	X					
ECOG Performance Status	X	X ⁵		Day 1 of each cycle	X	
SAFETY ASSESSMENTS						
Physical Exam, Weight, Height ¹⁷	X	X ⁵		Day 1 of each cycle	X	
Ophthalmologic Exam ⁶	X (≤35 days)			As clinically warranted	As clinically warranted	
Vital Signs ⁷	X	X	X	Day 1 of each cycle	X	X
12-lead ECG ⁸	X			Cycle 2 day 1, cycle 4 day 1, then every 12 weeks thereafter; more frequently if clinically warranted		X
ECHO or MUGA ⁹	X (≤35 days)			Cycle 2 day 1, cycle 4 day 1, then every 12 weeks thereafter; more frequently if clinically warranted		X ¹⁸
Adverse Events ¹⁰	X			Continuous		X
Concomitant Medications	X			Continuous		X
LABORATORY ASSESSMENTS						
Hematology/Chemistry ²²	X (≤14days)	X ⁵	X	Day 1 of each cycle or more often as clinically warranted	X	X
Coagulation/Urinalysis	X			As clinically warranted		X
Serum Pregnancy Test ¹¹	X (≤14 days)			Cycle 3, day 1, then every 8 weeks		X
Hepatitis B and Hepatitis C ¹⁶	X					
EFFICACY ASSESSMENTS						
Disease assessment/imaging studies	X ¹⁴			Every 8 weeks through week 56 then every 12 weeks thereafter (+/- 7 days)		X ¹⁵

STUDY PHASES ¹	SCR ²	TREATMENT-One Cycle=28 days			Follow up ³	
		D1	D15	Continuation	EOT	Post EOT FU
Visit Window (Days)	-28	N/A	±3	±3	± 3	±7
EXPLORATORY ASSESSMENTS						
Archival tumor tissue ¹⁹	X					
Optional Pre-Dose/Post-Dose Biopsies ¹²	X (≤28 days)		X ²⁰			
Blood Biomarkers	X		X			
Optional Post-Progression Tumor Biopsy ¹³					X	

SCR=Screening, D=Day

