Confirmation of CR and PR are required per protocol. Confirmation assessments must be performed no less than four weeks after the criteria for response have initially been met and may be performed at the next protocol scheduled assessment. If a confirmation assessment is performed prior to the next protocol schedule assessment, the next protocol scheduled evaluation is still required (e.g., evaluations must occur at each protocol scheduled time point regardless of unscheduled assessments).

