7.5.3.5 Evaluation of best overall response

The best overall response is the best response recorded from the start of the treatment until disease progression/recurrence and will be determined programmatically by the study investigator.

- To be assigned a status of SD, the post-baseline disease assessment must have met the SD criteria at least once after study Day 1.

CONFIDENTIAL

- If the minimum time for SD is not met, best response will depend on the subsequent assessments. For example if an assessment of PD follows the assessment of SD and SD does not meet the minimum time requirement the best response will be PD. Alternative subjects lost to follow-up after an SD assessment not meeting the minimum time criteria will be considered not evaluable.

Confirmation Criteria:

To be assigned a status of PR or CR, a confirmatory disease assessment should be performed no less than 28 days after the criteria for response are first met. Electronic scans will be required for independent review.

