13. DATA ANALYSIS AND STATISTICAL CONSIDERATIONS

13.1. Hypothesis

The primary objective is to determine whether trametinib is an effective targeted therapy in BRAF nonV600^{MUT} melanoma. The hypothesis described below will apply to cohort A ("high activity" mutations and fusion events). The null hypothesis is that the objective response rate (ORR; percentage of patients achieving a confirmed CR or PR is not attractive (defined as $\leq 5\%$). The alternative hypothesis is that the response rate is of interest for further development (defined as $\geq 25\%$).

The final analysis of the overall response rate will be performed using one sided test with $\alpha=0.05$. It is calculated that at least 4 responses are needed out of a total of 25 patients to reject the null hypothesis.

To allow early termination of the trial due to lack of efficacy, the trial will be conducted in two stages per Simon's Minimax Design. If no responses are demonstrated in the first 15 patients, then the trial will be terminated early for futility. If ≥ 1 responses are observed,

CONFIDENTIAL

enrollment will continue to 25 patients.

For the experimental arm (cohort B), the trial will also be conducted in two stages. If no responses are demonstrated in the first 15 patients, then the cohort will be terminated early for futility. If ≥ 1 responses are observed, enrollment will continue to a maximum of 25 patients. Additionally, when cohort A accrual has completed, cohort B will close and not accrue further patients.

Given the rapid changes in melanoma therapies, we will also have the option of closing either cohort if the clinical activity is low. If one or two responses occur in cohort A from the first 15 patients, the principal investigators and Coordinating Center will have the option of closing the trial at the interim analysis. The principal investigators must be in universal agreement for this to occur.

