13.4. Key Elements of Analysis Plan

Data will be listed and summarized according to the Novartis reporting standards, where applicable. Complete details will be documented in the Reporting and Analysis Plan (RAP). Any deviations from, or additions to, the original analysis plan described in this protocol will be documented in the RAP and final study report.

As it is anticipated that accrual will be spread thinly across centers and summaries of data by center would be unlikely to be information, data from all participating centers will be pooled prior to analysis.

All data up to the time of study completion/withdrawal from study will be included in the analysis, regardless of duration of treatment.

CONFIDENTIAL

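### The primary response-rate analysis may be run at 8 weeks, before a response first seen at the week-8 scan can be confirmed as the endpoint requires

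*Combined protocol and SAP*

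**What the plan says.** Section 13.1 defines the objective response rate as the "percentage of patients achieving a confirmed CR or PR". The null hypothesis is rejected with at least 4 responses in 25 patients.

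Section 7.5 states: "Confirmation assessments must be performed no less than four weeks after the criteria for response have initially been met". It allows confirmation to wait for the next scheduled scan. Section 7.5.3.5 repeats the rule: "a confirmatory disease assessment should be performed no less than 28 days after the criteria for response are first met". The Time and Events Table (section 7.1) schedules imaging every 8 weeks through week 56, with a 7-day window either side.

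On timing, section 13.3.2.1 states: "The primary analysis of ORR will be performed following treatment of all patients for at least 8 weeks or have discontinued therapy". Section 13.3.1 places the interim look after 15 subjects have had their first assessment, at 8 weeks.

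The stage 1 rule is worded in several ways. Section 5.1 stops the trial if fewer than one response is *confirmed*, and in the next sentence continues it if one or more are *observed*. Section 13.1 stops if none is *demonstrated* and continues if at least one is *observed*. Section 13.3.1 asks only for at least one response.

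**The concern.** The earliest permitted date for the primary analysis falls before the endpoint can normally be determined in the last patients enrolled. A patient who has just completed 8 weeks will usually have one post-baseline scan, or none if that scan falls late in its window. Such a patient cannot yet be a confirmed responder, yet stays among the 25.

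The error runs one way. True responders are missed, so the chance of overlooking an active drug rises. The design meets its power target by a very small margin, so there is little room for this.

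At stage 1 there is a related conflict. If the only response among the first 15 patients is awaiting confirmation, section 5.1 can be read both to stop and to continue. Only on the *confirmed* reading could Cohort A be closed with its sole response pending.

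**Working it through.** **Earliest confirmation.** First scan at week 8, plus 4 weeks, is week 12. If the first scan is 7 days early, 7 + 4 = week 11. At the next scheduled scan it is week 16, or week 17 at the end of the window. All are later than week 8.

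**Plan's own figures.** Inputs from sections 13.1 and 13.2: 15 patients in stage 1, continue with at least 1 response; 25 in total, reject with at least 4; rates 5% and 25%.

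P(reject) = Σ over x = 1 to 15 of P(Bin(15, p) = x) × P(Bin(10, p) ≥ 4 − x)

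At p = 0.25, the terms for x = 1, 2, 3 and x ≥ 4 are:

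0.0668 × 0.4744 + 0.1559 × 0.7560 + 0.2252 × 0.9437 + 0.5387 = 0.9008

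At p = 0.05 the sum is 0.0336. Early termination at 25% is 0.75^15 = 0.0134. These agree with Table 20 (0.901, 0.034, 0.013).

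**Effect of unconfirmable patients.** Let k be the number of the 10 stage 2 patients whose response could not yet be confirmed at the cutoff. Replace Bin(10, p) by Bin(10 − k, p). For k = 1 at p = 0.25:

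0.0668 × 0.3993 + 0.1559 × 0.6997 + 0.2252 × 0.9249 + 0.5387 = 0.8828

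Some responses might be confirmed early, for example in superficial lesions examined before week 8 (sections 7.5 and 7.5.1). If a share s of responses in those k patients is confirmed early, add an independent Bin(k, p × s) count.

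| k | Power, s = 0 | Power, s = 0.25 | Power, s = 0.50 | Type I error, s = 0 |
|---|---|---|---|---|
| 0 | 0.9008 | 0.9008 | 0.9008 | 0.0336 |
| 1 | 0.8828 | 0.8873 | 0.8918 | 0.0295 |
| 2 | 0.8615 | 0.8719 | 0.8820 | 0.0256 |
| 3 | 0.8367 | 0.8546 | 0.8713 | 0.0221 |
| 4 | 0.8078 | 0.8352 | 0.8597 | 0.0188 |

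At k = 1, power stays at 0.90 only if s is about 0.96 or more.

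**Plausible k.** The documents give no accrual rate, so these are assumptions. Take even accrual, with 4.345 weeks per month divided by the monthly rate as the spacing, and the last patient exactly at week 8. Count patients who have not reached week 12 (earliest usual confirmation) or week 16 (scheduled confirmation).

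| Cohort A accrual per month | Spacing (weeks) | k, week 12 | k, week 16 |
|---|---|---|---|
| 0.5 | 8.69 | 1 | 1 |
| 1 | 4.345 | 1 | 2 |
| 2 | 2.17 | 2 | 4 |

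k can be 0 if a discontinuation, not the 8-week mark, completes the trigger.

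**Stage 1, on the *confirmed* reading only.** Here k counts patients among the first 15. The probability of stopping at a true rate of 25% is 0.75^(15 − k): 0.0134, 0.0178, 0.0238, 0.0317 and 0.0422 for k = 0 to 4. Section 13.2 states less than 1.5%.

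**If stage 1 counts initial responses and the final test counts confirmed ones,** with follow-up complete, the error rates are bounded. Type I error is at most P(Bin(25, 0.05) ≥ 4) = 0.0341. Power lies between 0.9008 and P(Bin(25, 0.25) ≥ 4) = 0.9038. That reading costs nothing.

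**The case against.** The strongest reply is that 8 weeks is a floor, and the plan read as a whole points to a later analysis. Section 7.5.3.5 says: "The best overall response is the best response recorded from the start of the treatment until disease progression/recurrence". Section 13.4 says: "All data up to the time of study completion/withdrawal from study will be included in the analysis, regardless of duration of treatment". Section 6.4 allows for study completion "approximately 24 months after last subject first visit". An analyst could reasonably wait for confirmation, and the Reporting and Analysis Plan, to which section 13.3 leaves full details, may settle the cutoff.

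It stands that a later analysis is permitted. But these sections define what is counted, which data are included and when the study ends; none sets a cutoff for the response-rate analysis. If that analysis were meant to wait for study completion, the separate 8-week trigger would have no purpose. The Reporting and Analysis Plan is not among the documents, so what it says cannot be judged, and this limits confidence.

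The likely effect may also be small. High-activity mutations are rare (10 of 266 tumors in section 1.3.2), so slow accrual and k of 1 or 2 are plausible, a loss of about 2 to 4 points. The 80.8% figure needs 2 patients per month, confirmation only at week 16, and analysis exactly at the minimum. With design power at 0.9008, almost any loss crosses 90%. All of this stands.

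The stage 1 figures depend on one clause of section 5.1; the other wording favours continuing on an initial response. That also stands.

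Finally, week 16 is not the only workable cutoff, and it would still miss a recent patient who first responds at week 24. This is a fair limit on the remedy, but no reason to keep a trigger that precedes confirmation.

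**Conclusion.** The concern holds and should be fixed, with medium confidence. Followed at its permitted minimum, the stated timing rule would undercount confirmed responses in the most recently enrolled patients still on treatment. At a true rate of 25%, power would be 88.3% to 80.8% for k = 1 to 4, or 89.2% to 86.0% if half the responses in those patients were confirmed early, against the stated figure above 90%.

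This rests on an analysis at or near the minimum and on assumed accrual. Type I error falls from 3.4% to 2.9% (k = 1) and 1.9% (k = 4), so the risk is a missed active drug and not a false claim.

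The stage 1 point is secondary. On the *confirmed* reading the false-stop risk is 1.8% at k = 1 and 4.2% at k = 4; on the initial-response reading there is a conflict of wording and no excess risk. The sample size calculation itself is correct.

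**What to change.** 1. **Section 13.3.2.1.** Run the primary analysis once every treated Cohort A patient has reached the week-16 assessment, including its 7-day window, or has earlier progressed, died or discontinued. Follow any response pending at that point to its confirmatory scan.
2. **Sections 5.1, 13.1 and 13.3.1.** Adopt one stage 1 rule, at the sponsor's choice. Either state that stage 1 counts initial responses, or keep *confirmed* and do not declare futility while an initial complete or partial response among the first 15 patients awaits its confirmatory scan.

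**Cost.** The earliest primary analysis moves about 8 weeks later, or to the confirmatory scan of a response first seen at week 16. Stage 1 needs no delay under the initial-response rule; under the *confirmed* rule it waits only when the sole responses are pending. The 25 patients, the cutoffs (1 of 15, 4 of 25) and the scan schedule stay as they are.

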13.3.2.2. Secondary Analyses

13.3.2.2.1. Cohort B

Overall response rate will be assessed in cohort B as defined by RECIST 1.1 criteria and will be reported in a descriptive fashion. No statistical comparisons will be performed.

CONFIDENTIAL

13.3.2.2.2. Overall Survival and Progression-Free Survival for both cohort A and B

Overall survival, defined as the time from Day 1 of the trametinib therapy to death from any cause. Progression free survival, defined as the time from Day 1 of trametinib therapy to progression of disease as defined by RECIST 1.1 criteria or death, will be reported for each arm. We will also perform subset analysis for PFS stratified by baseline characteristics including LDH level, metastatic stage, and previous therapy (particularly whether a subject has received immune-based therapy).

13.3.2.2.3. Safety

Adverse events (AEs) will be coded using the standard MedDRA and grouped by system organ class. Adverse events (AEs) will be graded by the investigator according to the National Cancer Institute- Common Toxicity Criteria for Adverse Events (NCI-CTCAE), (version 4.0).

Events will be summarized by frequency and proportion of total subjects, by system organ class and preferred term. Separate summaries will be given for all AEs, treatment-related AEs, serious adverse events (SAEs) and AEs leading to discontinuation of study treatment. Adverse events (AEs), if listed in the NCI-CTCAE (version 4.0) will be summarized by the maximum grade. Otherwise, the AEs will be summarized by maximum intensity.

Characteristics (e.g. number of occurrences, action taken, grade, etc.) of the following AEs of special interest will be summarized separately.

The incidence of deaths and the primary cause of death will be summarized.

13.3.2.2.4. Biomarkers and Pharmacodynamic Analyses

The study will analyze tumor tissue and/or blood to understand genetic mechanism of MEK inhibitor response and resistance. As data warrant, correlation analysis will be performed to explore the relationship between patient's biomarker and PD data (e.g. change from baseline) to patient's tumor response. As data warrant, additional analysis will be conducted on cfDNA data. Full details will be provided in RAP prior to study initiation.

Molecular characterization of tumor tissue will be performed to identify markers that correlate with clinical responsiveness to treatment with trametinib. Analysis will incorporate detection of DNA-based alterations in other genes known to be altered in melanoma, including (but not limited to) genes in the MAPK pathway (i.e. MEK1/2, NF1), PI3K-AKT pathway (i.e. PIK3CA, AKT, PTEN), cell cycle regulators (i.e. CDKN2A, CDK4, CCND1), and/or broader molecular testing. Analysis of RNA and protein may also be performed for tumors with sufficient material available to assess functional networks and pathways. The exact methodologies used will be selected based on the DNA/RNA/protein amounts, technologies, and information available at the time the analyses will be performed. Analyses will be performed on pre-treatment and/or archival samples to identify predictors of treatment outcomes. Optional on-treatment biopsies will be used to evaluate pharmacodynamic and other molecular effects of

CONFIDENTIAL

treatment, which will be compared to clinical outcomes. Optional post-progression samples will be analyzed to identify mechanisms of resistance.

13.3.3. Withdrawal

Reason for subject withdrawal will be listed.

13.3.4. Missing Data

Missing data will not be imputed. Where appropriate, available data will be summarized over specified intervals (e.g., from start of treatment until withdrawal from study) using suitable summary statistics.

13.3.5. Protocol Violations

A summary and listing of protocol violations will be provided.

13.3.6. Assessment Windows

Safety assessments that occur prior to the administration of study drug will be considered screening assessments. Safety assessments that occur after dosing has begun will be considered as having occurred while on treatment.

Disease assessments will be distinguished as belonging to either screening, continued therapy or post-study phases of the study.

13.3.7. Other Issues

Data from participating centers will be pooled prior to analysis. It is anticipated that subject accrual may be limited across centers and summaries of data by center would likely not be informative. Therefore, these summaries will not be provided.

Demographic and baseline characteristics will be summarized.

13.4. Key Elements of Analysis Plan

Data will be listed and summarized according to the Novartis reporting standards, where applicable. Complete details will be documented in the Reporting and Analysis Plan (RAP). Any deviations from, or additions to, the original analysis plan described in this protocol will be documented in the RAP and final study report.

As it is anticipated that accrual will be spread thinly across centers and summaries of data by center would be unlikely to be information, data from all participating centers will be pooled prior to analysis.

All data up to the time of study completion/withdrawal from study will be included in the analysis, regardless of duration of treatment.

CONFIDENTIAL

13.4.1. Pharmacodynamic Analyses

13.4.1.1. Translational Research Analyses

The results of translational research investigations may be reported separately from the main clinical study report (CSR). All endpoints of interest from all comparisons will be descriptively and/or graphically summarized as appropriate to the data.

Further details on the translational research analyses will be addressed in the Reporting and Analysis Plan (RAP).

13.4.1.2. Novel Biomarker(s) Analyses

The results of these biomarker investigations may be reported separately from the main clinical study report. All endpoints of interest from all comparisons will be descriptively and/or graphically summarized as appropriate to the data.

Additional exploratory analyses may be performed to further characterize the novel biomarker.

14. STUDY CONDUCT CONSIDERATIONS

14.1. Posting of Information on Clinicaltrials.gov

Study information from this protocol will be posted on publicly available clinical trial registers before enrolment of subjects begins.

14.2. Regulatory and Ethical Considerations, Including the Informed Consent Process

Prior to initiation of a study site, the Coordinating Center will obtain approval from the appropriate regulatory agency to conduct the study in accordance with International Conference on Harmonization Good Clinical Practice (ICH GCP) and applicable country-specific regulatory requirements.

The study will be conducted in accordance with all applicable regulatory requirements.

The study will be conducted in accordance with ICH GCP, all applicable subject privacy requirements, and the ethical principles that are outlined in the Declaration of Helsinki 2008, including, but not limited to:

- Institutional review board (IRB)/ethics committee (EC) review and approval of study protocol and any subsequent amendments
- Subject informed consent
- Investigator reporting requirements

The Coordinating Center will provide full details of the above procedures, either verbally, in writing, or both.

CONFIDENTIAL

Written informed consent must be obtained from each subject prior to participation in the study.

Protocol Review and Amendments

Information regarding study conduct and progress will be reported to the Institutional Review Board (IRB) per the current institutional standards of each participating center.

Any changes to the protocol will be made in the form of an amendment and must be approved by the IRB of each institution prior to implementation.

The Protocol Chair (or his designee) is responsible for the coordination and development of all protocol amendments, and will disseminate this information to the participating sites.

Before implementing this study, the protocol, the proposed informed consent form and other information to subjects, must be reviewed by a properly constituted Institutional Review Board/Independent Ethics Committee (IRB/IEC/REB). A signed and dated statement that the protocol and informed consent have been approved by the IRB/IEC/REB must be given to the Coordinating Center before study initiation. Any amendments to the protocol, other than administrative ones, must be approved by this committee.

Amendments significantly affecting the safety of subjects, the scope of the investigation or the scientific quality of the study, require additional approval by the IRB/IEC/REB. A copy of the written approval of the IRB/IEC/REB, must be sent to the Coordinating Center.

Amendments affecting only administrative aspects of the study do not require formal protocol amendments or IRB/IEC/REB approval but the IRB/IEC/REB of each site must be kept informed of such administrative changes.

Protocol Deviations

The Coordinating Center is responsible for implementing and maintaining quality assurance and quality control to ensure that studies are conducted according to the protocol, GCP, and all applicable regulatory requirements. A protocol deviation is any noncompliance with the protocol. Noncompliance can be on the part of the study participant, the Investigator, or the study site staff. Deviations to the protocol are not permitted except when necessary to eliminate an immediate hazard to study subjects.

